- report 40 or more days of cannabis use in the past 90 day;
- have smoked at least seven cigarettes in the past seven days;
- have been smoking for at least the past year;
- can speak and write fluent conversational English;
- are between 18 and 70 years of age; and
- are willing to make an attempt to quit both cannabis and tobacco smoking.

Participants will be excluded for the following:

- expected to have unstable medication regimen during the study;
- currently receiving non-study behavioral treatment for cannabis use disorder or smoking;
- myocardial infarction in past six months;
- contraindication to NRT with no medical clearance;
- use of other forms of nicotine such as cigars, pipes, or chewing tobacco with unwillingness to stop use of these forms;
- current pregnancy;
- primary psychotic disorder or current manic episode;
- substance use disorder (other than mild alcohol use disorder, cannabis use disorder or nicotine use disorder) within the preceding three months; or
- current imprisonment or psychiatric hospitalization.

Recruitment

Participants will be recruited from primary care and substance use clinics at Duke University Medical Center (DUMC). Flyers and brochures will be placed in DUMC clinic areas, and may also be placed in community settings such as local restaurants and grocery stores. We will also advertise in local newspapers and online classified services such as www.craigslist.com. With permission from area

colleges and universities (and their respective IRBs where required), we will post flyers and brochures on area campuses. We will contact administrators and/or clinicians at local area community health centers, including Lincoln Community Health Center. Upon approval by the Durham Veterans Affairs (VA) Medical Center IRB, we will post flyers and brochures at that facility and its community-based outpatient clinics. Any flyer posted at the VA-owned facilities will include the following statement: "This is not VA research, will not be conducted by VA, has not been reviewed by VA's Institutional Review Board, and is not endorsed by VA. VA is not responsible for any costs incurred by a Veteran if the Veteran enters the study as a research subject. The announcement is being provided for information only."

Participants who find the study on clinicaltrials.gov and emails study staff will be sent an email to contact the study coordinator by telephone.

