application (mCM) targeting BOTH smoking and cannabis use. Treatment components are separately described herein. Table 1 provides a summary of study visits, procedures, and compensation.

Table 1. Stu	Table 1. Study Procedures						
Session	Tasks	Time	Payment				
1 (lab)	Consent	30 min	\$100				
	Screening (clinical interview, questionnaires,	3 ½ hours					
	impulsivity tasks)						
	Urine sample, breath sample taken						
	Counseling session 1						
	mCM equipment training						
2 (phone)	Counseling session 2	30 mins.	None				
3 (phone)	Counseling session 3	30 mins.	Up to \$49 for monitoring				
	Begin practice mCM for 1 week		between 3 & 4				
	Begin bupropion if using						
4 (phone)	Quit day	30 mins.	Up to \$402.50 for 2 weeks				
	Counseling session 4		monitoring between 4 & 5				
	Begin abstinence mCM						
	Begin NRT						
5 (phone;	Counseling session 5	30 mins.	Up to \$892.50 for 2 weeks				
2 wks post	Continue abstinence mCM		monitoring between 5 & 6				
session 4)	Reduce NRT to 14 mg						
	Continue use of "rescue" NRT PRN						
6 (phone;	Quick phone check-in	10 min	Up to \$98 for monitoring				
2 wks post	Continue mCM wash-out period		between 6 & 7				
session 5)	Reduce NRT to 7 mg						
	Continue use of "rescue" NRT PRN						
7 (lab; 2	Feasibility interview, question naires,	1 hour	\$35 for returned				
wks post	impulsivity tasks		equipment, \$100 for				
session 6)	Saliva sample, CO reading, and urine drug		session				
	screen Prompt to return equipment						
	Cease NRT						
8 (lab; 3	Questionnaires, impulsivity tasks	30 min	\$100				
month	Saliva samples, CO readings, and urine drug						
follow-up)	screens						
9 (lab; 6	Questionnaires, impulsivity tasks	30 min	\$100				
month	 Saliva samples, CO readings, and urine drug 						
follow-up)	screens						
	Cease bupropion						
		TOTAL	Up to \$1,877				

Measures. At the screening visit, participants will provide sociodemographic data on age, gender, education, income, ethnicity, marital and employment status. They will be interviewed using the substance use disorders section and the psychotic and associated symptoms section of the Structured Clinical Interview for DSM-5 (SCID-5; First, Williams, Karg, & Spitzer, 2015). Participants will also

complete the following measures:

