Pharmacotherapy for Smoking Cessation. Participants will receive standard pharmacotherapy for smoking cessation. Study medications will be mailed to participants after the screening visit. Study medications consist of bupropion, an 8-week course of nicotine patch use and up to two rescue methods (e.g., nicotine gum, lozenge). Participants will be screened for suitability for nicotine replacement therapy (NRT) or other smoking cessation medication, and the study physician will determine safety for NRT and bupropion use. Participants will receive tailored amount and delivery type of NRT based on number of cigarettes smoked per day using an established protocol (Bars et al., 2006). Bupropion will be prescribed to start one week prior to their quit day [150 mg/daily for days 1-7 and 300 mg/daily (administered in two daily doses) until the 6-month follow-up. If a participant with a seizure disorder, history of or current hepatitis and/or cirrhosis, renal impairment, and/or uncontrolled diabetes wishes to enroll in the study, he/she will not receive contraindicated medications. If a participant with any of these medical conditions is unwilling to participate in the study without taking bupropion, he/she will be withdrawn from the study.

Follow-Up Visits. Participants will be asked to attend three follow-up visits at end of treatment, 3- and 6-months post-quit. At the follow-up visits, participants will be asked about their experiences with various treatment components. These will include closed ended questions and open-ended interview

questions. In addition, the study coordinator will ask questions about alliance with the study therapist. Participants will be asked to complete symptom self-report measures and computerized impulsivity tasks at each follow-up visit. Participants will be asked about smoking and cannabis use in the period since the quit date. Self-reported abstinence will be bioverified by several means. Self-reported prolonged abstinence from cannabis use will be verified by urine and OF cannabis assessments. Self-reported abstinence from smoking will be verified by saliva cotinine assay and CO reading.

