Participants will be offered NRT, and there are risks associated with the use of NRT. Minimal risks associated with wearing a nicotine patch include skin irritation, dizziness, lightheadedness, increased heart rate or blood pressure, nausea or vomiting. If a participant indicates a contraindication to NRT (e.g. uncontrolled hypertension), medical clearance for NRT will be sought from the participant's primary care physician and/or the study physician. If a participant with a seizure disorder, history of or current hepatitis and/or cirrhosis, renal impairment, and/or uncontrolled diabetes wishes to enroll in the study, he/she will not receive contraindicated medications.

Participants who are medically eligible will also be prescribed bupropion SR. Risks of bupropion use include dry mouth, insomnia, nausea, constipation, headache, shakiness or jitteriness, skin rash, sweating, allergic reaction, change in appetite, weight loss, dizziness, tremor, thinking abnormally, hot flashes, worsening depression or suicidal thoughts and behavior, and ringing in the ears. At the highest dosage of bupropion to be used in this study, seizures occurred in 1 out of every 1000 (0.1%) who took this drug. Participants are informed that they are not required to take bupropion, and will be allowed to participate in the study if they refuse to do so.

There is a potential risk associated with the loss of confidentiality of study data. Specifically, collection and transfer of videotaped carbon-monoxide monitoring have risks with regards to privacy and confidentiality. Please see "Protection From Risk: Data Security" for details on reduction of risk with regards to the proposed videotaping.

Protection From Risk: Data Security

While participants may benefit from quitting smoking and marijuana use, there are no guaranteed benefits to the individual participant and no immediate benefits of the proposed research to others. There are potential benefits to others from the information generated that potentially will be helpful in developing new combined treatments for smoking and marijuana use. In our opinion, the anticipated benefits of this study outweigh the potential risks. The study is completely voluntary and participants are informed that they are free to refuse to answer any items on the questionnaires or questions from the interview. They are also informed that they are free to decline participation in procedures and can withdraw from the study at any time.

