semi-parametric methods (e.g. quasi-likelihood methods; McCullagh & Nelder, 1989). In planning a full RCT of the tele-health mCM intervention for CUD and smoking, it is important to evaluate study feasibility and treatment procedures, as well as gaining information about effects on proposed outcome variables. To remain consistent with guidelines for designing and evaluating pilot studies, analyses will be primarily descriptive (Thabane et al., 2010) and aimed at informing feasibility and needed modifications rather than detecting statistically significant between-group differences (Leon, Davis, & Kraemer, 2011). However, to best utilize participant data to optimally design the treatment, we have established several objectives to indicate whether the planned trial is feasible.

Feasibility of cannabis abstinence assessment will be based on data from this pilot. While the validity of the Alere Oratect Oral Fluid Drug Screen Device has demonstrated excellent agreement with clinical samples analyzed with GC/MS methods, the utility of using daily saliva tests and CO (which measures carbon monoxide for cannabis smoking in the past 3 hours) has not been evaluated. We will examine the utility of the proposed saliva testing protocol. Additionally, qualitative data on the use of saliva tests will be examined to ensure that participants find it acceptable and preferable to in-clinic assessment methods.

The feasibility and acceptability of the multi-component tele-health mCM intervention will be assessed. We will collect frequency data regarding the number of videos transmitted, number of study measures completed at each time point, the amount of missing data (including missed videos), the number of sessions attended, and the frequency and severity of adverse events. We will assess the association of potential stratification variables (sociodemographic, psychiatric, and CUD/smoking severity variables) with feasibility indices, adherence to study protocol (video transmission, completion of study measures at each time point, session attendance), attrition, and adverse events. We will also determine whether attrition rates and frequency and severity of adverse events exceed those of previous smoking treatment trials. These data will provide important information useful in refining the intervention and associated assessments/procedures prior to their implementation in a larger-scale RCT.

References

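### Table 1 gives one fixed nicotine replacement (NRT) sequence with no starting amount, while the text tailors the amount to cigarettes per day; nothing joins the two, so "Reduce NRT to 14 mg" is a reduction only if every NRT user starts above 14 mg

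*Combined protocol and SAP*

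**What the plan says.** Three places in the combined protocol and SAP bear on the NRT amount.

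- **Procedures, Table 1.** NRT begins at session 4 (quit day), with no amount. Session 5, two weeks later, carries the row "Reduce NRT to 14 mg". Session 6, two weeks after that, carries "Reduce NRT to 7 mg". NRT stops at session 7, a further two weeks on. None of these rows is limited to a subgroup.
- **Pharmacotherapy for Smoking Cessation.** "Participants will receive tailored amount and delivery type of NRT based on number of cigarettes smoked per day using an established protocol". The protocol is cited, but its dose bands are not reproduced. The same section describes the study medication as bupropion plus "an 8-week course of nicotine patch use and up to two rescue methods", with gum and lozenge as examples of rescue products, and says that "the study physician will determine safety for NRT and bupropion use".
- **Participants.** The smoking criterion is to "have smoked at least seven cigarettes in the past seven days", with no upper limit.

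Potential Risks adds: "Participants will be offered NRT, and there are risks associated with the use of NRT". NRT is therefore offered, subject to screening, and is not assumed for all enrolled participants.

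**The concern.** The text makes the amount of NRT depend on how much a person smokes. From session 5 the table gives one figure regardless of smoking level. Because entry reaches very light smokers and has no ceiling, a rule tied to cigarettes per day could produce a wide spread of amounts. The table neither acknowledges that spread nor says when tailoring ends.

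Two things are at stake. The first is participant safety: staff working from the table and staff working from the text could arrive at different amounts for the same person, and the documents do not say which place governs. The second is what the pilot can report. It is meant to inform a larger trial and to summarise the frequency and severity of adverse events. If the NRT component is not fixed by one rule, the treatment delivered cannot be described or repeated exactly.

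**Working it through.** The plan states no figure to reproduce, and no power or error rate is involved: Data Analyses says that "analyses will be primarily descriptive". The check compares the passages and uses simple arithmetic.

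**1. Entry floor (Participants).** 7 cigarettes / 7 days = 1.0 per day on average.

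**2. Session 5 step (Table 1).** Let D be the starting amount in mg. The change at session 5 is 14 - D. The documents give no value for D, so the values below are assumptions that show the range.

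| Assumed start D (mg) | Session 5 change, 14 - D (mg) | Session 6 change, 7 - 14 (mg) |
|---|---|---|
| 7 | +7 | -7 |
| 14 | 0 | -7 |
| 21 | -7 | -7 |
| 28 | -14 | -7 |
| 35 | -21 | -7 |
| 42 | -28 | -7 |

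The session 5 row is a reduction if and only if D > 14. Session 6 is a 7 mg reduction for any D once session 5 has been followed as written.

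**3. Does the table follow the tailoring rule?** Under the text, two people who smoke different numbers of cigarettes per day may be given different amounts. Under the table, both are on 14 mg after session 5 and 7 mg after session 6. This holds even if every start exceeds 14 mg. The table and text can be read together only by supposing that tailoring sets the starting amount alone and ends at session 5, and no section says so.

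**4. Are the mg rows meant to be conditional?** Table 1 does mark conditions elsewhere: the bupropion start is limited to those using it, and rescue NRT is marked as needed. The mg rows carry no such mark.

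**5. Duration.** The Table 1 intervals from session 4 to session 7 sum to 2 + 2 + 2 = 6 weeks. The text gives an 8-week patch course. The gap is 8 - 6 = 2 weeks.

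**The case against.** The strongest reply is that the two places may be compatible. The text gives no NRT dose and the table gives no starting dose, so tailoring could set the start and the rescue products while the table gives the later taper. If all tailored patch starts exceed 14 mg, the session 5 wording is right for everyone using NRT. Table 1 is also introduced as a summary, the study physician decides on safety, and a row that says to reduce would not naturally lead staff to raise a dose. No planned analysis uses NRT dose.

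Much of this stands, and it rules out several stronger readings that a reader might infer:

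- *That the schedule raises the dose of light smokers.* This needs a tailored start below 14 mg. The documents give neither a starting dose nor the cited protocol's bands, so it is a possibility left open and not a demonstrated event.
- *That every participant is affected.* NRT is offered after screening and is subject to the study physician's decision, so the point concerns NRT users only.
- *That the mg steps are meaningless for someone not on a patch.* The text describes a patch course with gum or lozenge as rescue, and the table keeps rescue NRT on its own line. No section describes an NRT user without a patch.
- *That session 6 has the same fault.* It is a true reduction once session 5 has been followed.

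The reply does not supply the missing link. The compatible reading has to be constructed by the reader, and its key condition, all starts above 14 mg, is stated nowhere. Physician oversight does not fill the gap either: the documents give the physician a safety decision but do not assign anyone to adjust the session 5 step, which falls at a telephone contact.

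**Conclusion.** The concern holds as a failure to reconcile Table 1 with the pharmacotherapy text. This part rests on the wording alone: the table's fixed, unconditional amounts from session 5 do not follow the rule that the amount depends on cigarettes per day, and no section connects them.

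The possible size of the discrepancy at session 5 rests on assumed starting amounts: -7 mg from 21, no change from 14, +7 mg from 7. The wording at that step is correct only if every NRT user starts above 14 mg, which the documents neither state nor rule out. They also give no basis for estimating how many of the up to 10 enrolled participants would be affected, and the number could be zero. The 2-week difference in NRT duration follows directly from the stated intervals and needs no assumption.

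The point should be corrected before the schedule is used, because it bears on participant safety and on which treatment is delivered. It does not undermine the descriptive analysis, and it implies no view on which dose or schedule is right.

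**What to change.** The sponsor and study physician should reconcile Table 1 with Pharmacotherapy for Smoking Cessation so that one rule determines each NRT user's amount across sessions 4 to 7. The revised text should say:

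- how the tailored starting amount joins the later steps;
- whether the mg rows at sessions 5 and 6 apply to all participants using NRT or only to some tailored starting amounts;
- how long NRT lasts, so that the 6 weeks implied by the table and the 8-week patch course in the text agree.

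Which rule holds is for the sponsor and study physician to decide. The cost is one wording edit to the table and the text, with no added visits, staff or participants.

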mCM Procedures. As part of previous projects (see Duke PRO00031703, PRO00050835, PRO61683, and PRO00062101), we developed a smart phone app that allows CM to be used outside the clinic to address substance misuse. Our programmer has completed adaptation of our existing mCM application to integrate the assessment of cannabis abstinence into the design of the app. Though most of the procedures used in our previous mCM studies are easily applied to CUD, we have made several important changes. We have added a videotaped OF assessment in which participants record themselves self-administering a OF test kit. For each OF video recording, each participant will be asked to 1) begin a recording using the smartphone device; 2) show the unused test strip to the camera; 3) swab his or her cheek while on camera; and 4) place the strip on a flat surface for 5 minutes and 5) show the final result to the camera. Saliva sticks will be numbered so that the number associated with the saliva swab can be ensured to be the number of the swab result. Participants will provide a CO reading and THC OF reading twice daily. Because reinforcers are most effective when delivered immediately after the target behavior is performed (Lattal, 2010), the phone app provides daily feedback on abstinence status, financial amount earned, and how the amount was calculated.

Video recordings will be made using a DROID MAXX 2 with an octa-core 1.7 Ghz processor, 2 GB RAM, and 5.5" full HD display. The operating system (OS) being utilized for the smart phones is Android 5.1.1 Lollipop, see FIPS 140-2 certificate 1998. The CO breath monitor, the iCO Smokerlyzer, is a battery

operated instrument that measures CO in ppm

(http://www.bedfont.com/shop/smokerlyzer/ico_smokerlyzer). The Bedfont/coVita iCO™ Smokerlyzer® plugs into a smart phone by means of the headphone jack, and communicates with the smart phone app developed by our team. Participants are able to see the CO reading within the app, and the app collects the CO data directly. Data are stored in the same manner as the videorecordings that participants upload (see below and in "Protection From Risks: Data Security" herein).

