With regards to FDA device issues, Bedfont/coVita will not be seeking 510k Clearance on the iCO™ Smokerlyzer® because it does not meet the standard/criteria of a medical device. Device manufacturers are required to follow FDA guidance to inform them of when a device necessitates 510k application. Per [name] at Bedfont/coVita, their regulatory team has determined that this is not necessary primarily because they do not make a medical claim about the device, as it is not designed to diagnose a disease or illness. Simply measuring CO is not diagnosing a disease or illness and Bedfont/coVita makes no medical claim that the iCO™ Smokerlyer® can be used to screen for CO poisoning.

We will compare self-reports to objective measures of cannabis use during the abstinence period. Feasibility of using proposed methods will be based on the observed concordance of self-report, CO readings, and saliva testing in the early abstinence period. If saliva tests taken before bedtime do not coordinate with participants' self-report during early abstinence weeks 1-2, we will modify procedures for subsequent weeks in order to 1) increase frequency of monitoring and 2) have the timing less predictable; e.g., more frequent cannabis readings will occur randomly between 8am-11pm, clustered in the evenings (8pm-11pm) and weekends (Friday-Sunday) (Alessi & Petry, 2013). While potentially more burdensome, this modification will be designed to alarm-prompt readings to occur up to 14 occasions each week to ensure adequate coverage. This procedure is designed to ensure that participants do not know when they will have a long time period between readings that would provide an opportunity for using cannabis that would be metabolized before the next reading. When prompted, participants will have one hour to submit their sample, with a reminder prompt at 30 minutes. Similar procedures have produced good adherence in previous research (Alessi & Petry, 2013). At the end of the monitoring period, qualitative data will be collected assessing bio-verification preferences, barriers, and any attempts to tamper or alter samples.

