Regarding mobile information security, we have taken care in previous projects using similar methods and technology to develop procedures to limit the risk of breach of confidentiality and privacy. For example, the smart phone is programmed such that a staff member will set up the telephone and enter the participant's code into the phone. When uploading a video, participants upload directly from the phone to an approved website that has been vetted by Duke's information security officers, and the phone programming ensures that the video is uploaded into the correct participant's area of the website. This ensures that study participants' data is stored in the correct place, and that study participants cannot view any other participants' data. Participants are asked to review their videos before posting, and they can choose not to upload any video that they don't wish to upload for any reason. In previous studies that have been run using this methodology, we have had no participant complaints regarding issues of privacy and confidentiality related to use of the smart phone videotaping procedures. In order to enhance participants' privacy, we will restrict access to several of the telephone's ancillary applications, and we have the ability to remotely delete data from any phones that are not returned to the study team.

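### Home saliva/CO feasibility is judged on uploaded readings only, participants can see a saliva result before choosing not to upload it, and no planned analysis relates missed videos to diary-reported use or to concordance

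*Combined protocol and SAP*

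**What the plan says.** The protocol's mCM Procedures section states the criterion: "Feasibility of using proposed methods will be based on the observed concordance of self-report, CO readings, and saliva testing in the early abstinence period". It announces a wider comparison as well: "We will compare self-reports to objective measures of cannabis use during the abstinence period". The trigger for more frequent and less predictable monitoring compares bedtime saliva tests with participants' "self-report during early abstinence weeks 1-2". No agreement statistic, threshold, denominator or rule for missing readings accompanies the criterion.

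The same section schedules saliva and CO readings twice a day over three phases: a practice week paid for completing readings, four weeks paid for abstinence, and two weeks in which payment no longer depends on abstinence. Table 1 calls the last phase the wash-out. Weeks 1-2 after quit day are the first half of the paid-for-abstinence phase. An evening diary on cigarettes and on smoked, ingested and vaped cannabis runs through all three phases.

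In each saliva recording the participant waits for the strip to develop and must then "show the final result to the camera". Under Protection From Risk: Data Security, participants review their videos before posting, and "they can choose not to upload any video" they do not wish to send. For CO, "the app collects the CO data directly", but the text adds: "Data are stored in the same manner as the videorecordings that participants upload". It is therefore unclear whether a CO value is kept when the saliva video is not sent.

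Three provisions bear on missing or altered readings. Participants are asked at the end of monitoring about "any attempts to tamper or alter samples". The Data Analyses section (printed twice, before and after the reference list) counts missed videos. It also relates video transmission to sociodemographic, psychiatric and severity variables.

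**The concern.** Concordance can be computed only on readings that arrive. A participant who has used cannabis during the contingent weeks sees the positive strip before deciding whether to send the video, so missing saliva results may depend on their own value. The plan's criterion and its weeks 1-2 trigger both read the agreement figure without reference to what was not sent.

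Evaluating the bioverification method is a stated purpose of the pilot, and the answer is meant to support a larger study. High agreement among uploaded readings could mean that the test tracks use, or that some readings showing use were not sent. In the second case the trigger might not fire when it should. The diary data that would help to separate the two are already collected, but no planned analysis sets them against upload status.

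**Working it through.** The documents give no concordance figure to reproduce, so the check is how far missing readings can move the figure.

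**Inputs from the documents.** Goal of 5 completers, up to 10 enrolled (Participants). Two readings a day (mCM Procedures). Video adherence of 92% and 93% in the two preliminary studies, which used CO videos (Preliminary Data).

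**Step 1: number of readings.** Weeks 1-2 give 5 × 2 × 14 = 140 scheduled saliva readings for 5 completers, or 280 for 10 participants. Bedtime readings alone, which the trigger uses, number 5 × 14 = 70 for completers.

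**Step 2: range over all scheduled readings.** With upload fraction a and observed concordance c, concordance over everything scheduled lies between a·c (all missing discordant) and a·c + (1 − a) (all missing concordant).

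- a = 0.92, c = 0.90: 0.828 to 0.828 + 0.08 = 0.908.
- a = 0.93, c = 0.90: 0.837 to 0.837 + 0.07 = 0.907.
- a = 0.80 (assumed), c = 0.90: 0.720 to 0.720 + 0.20 = 0.920.
- In counts (hypothetical): 7% of 70 bedtime readings is about 5 missing. If 62 of the 65 uploaded agree, the observed figure is 95.4% and the range is 62/70 = 88.6% to 67/70 = 95.7%.

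**Step 3: direction.** Assume, for illustration only, that 20% of scheduled saliva tests are positive, half of those fall on days when the diary reports use, and 95% of negatives fall on days when it does not. Per 100 readings: 10 positive with use reported, 10 positive with use denied, 4 negative with use reported, 76 negative with no use reported. Full-data agreement is (10 + 76)/100 = 86.0%. Positive agreement (saliva positive among readings on diary-reported use-days) is 10/14 = 71.4%. Now remove 8 positives, to match 92% upload:

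| Which 8 are missing | Observed agreement | Positive agreement | Range over all 100 |
|---|---|---|---|
| All denied in diary | 86/92 = 93.5% | 10/14 = 71.4% | 86% to 94% |
| 4 denied, 4 admitted | 82/92 = 89.1% | 6/10 = 60.0% | 82% to 90% |
| All admitted in diary | 78/92 = 84.8% | 2/6 = 33.3% | 78% to 86% |

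Observed agreement can rise or fall. The range contains the full-data 86% in every row: at the bottom, inside, and at the top. Positive agreement reacts when admitted positives are missing and not when denied ones are.

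**Step 4: why counting missing as positive is not a bound.** A missing reading counted as positive becomes concordant on a day when the diary admits use. In the same example, suppose only the 4 negatives on diary-reported use-days are missing, for technical reasons. Counting them as positive gives (86 + 4)/100 = 90%, above the full-data 86%. The a·c limit gives 86/100 = 86%.

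**Step 5: what the planned association covers.** It asks which kinds of participant send fewer videos. It does not ask whether a given day's missing video falls on a day of reported use, which is the question that bears on concordance.

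**The case against.** The strongest reply is that nothing shows a reason to withhold. The documents do not say how a missed video affects earnings, so it is not established that a missed reading is treated better than a positive one. The diary pays the same whatever the answer, which weakens the case for assuming denial. In the second preliminary study 93% of videos were sent although only 50% of participants were abstinent at four weeks. Even if all the missing 7% came from the other half, that half would have sent 1 − 0.07/0.50 = 86%. Those were CO videos and the two measures differ, so this is suggestive only, but it counts against large-scale withholding.

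It is also fair to say that missed videos are not ignored, that tampering is asked about, and that this is a small descriptive pilot in which about five missing bedtime readings may be all there is to tabulate.

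These points limit the size of the concern and rule out a claim that bias is present. They do not answer it. The criterion still rests on uploaded readings, the route by which results could go missing selectively is written into the procedures, and neither the participant-level association nor the end-of-monitoring questions connect missing readings to that day's use. With so few readings, a handful missing can move the figure by several points.

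**Conclusion.** The point holds as a gap in the analysis plan, at the level of a recommended change and with moderate confidence. At the upload rates of the preliminary studies, the uncertainty from missing readings is 7 to 8 percentage points wide, and at an observed 90% nearly all of it lies below the observed figure. It widens in step with the missing fraction. The direction and size of any actual distortion rest on assumed use and denial rates and are not known.

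A reader might infer more than the documents support:

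- That participants do withhold positives, or that the concordance figure will be inflated. Withholding is only possible, and agreement can also fall.
- That contingent and non-contingent weeks are pooled in the criterion. The weeks 1-2 window lies wholly in the contingent phase; what is absent is a contrast with the other three weeks.
- That CO would reveal denied cannabis use. CO also reflects tobacco in these dual smokers and, as the Background says, misses vaped and ingested cannabis.
- That the feasibility conclusion would change. No threshold is stated, so this cannot be shown.

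**What to change.** Amend mCM Procedures and Data Analyses as follows, using data already collected.

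1. Cross-tabulate the saliva result (negative, positive, not uploaded) against that day's diary-reported cannabis use. Report positive agreement on diary-reported use-days beside overall agreement. This shows missing readings on days of admitted use; it cannot show missing readings on days of denied use.
2. Beside the observed concordance c at upload fraction a, report the range from a·c to a·c + (1 − a) over all scheduled readings. This covers denied use as well. If missing is also counted as positive, label that a sensitivity scenario and not a bound. Read these figures when applying the weeks 1-2 trigger and when stating feasibility.
3. Show concordance and upload rate descriptively for the practice, contingent and wash-out weeks, noting that the practice week is pre-quit training data with a different prevalence of use.

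CO may be shown as supporting information only, with a statement of whether the app keeps it when the saliva video is not sent.

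The cost is a few descriptive tables and a concordance figure that may look less favourable. No extra visits, tests, diary items or participants are needed.
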